#### Visit 2: 4 weeks (approx.) following Visit 1: (approximately 30minutes)

- Confirm Eligibility
- Oral hard and soft tissue examination
- Completion of questionnaire with regards to current oral health/hygiene practices (Part A) and attitudes to oral health (Part B). (See Appendix 2)
- Final intra-oral scan download patient report
- Final plaque scores and gingival health assessments
- Provision of pictorial oral health report for patient to take away.
- For participants assigned to the standard verbal OHI alone, review of patient pictorial report obtained at Visit 1 and Visit 2 and provision of tailored OHI advice and a copy of their pictorial report, provision of mouth mirror and leaflet on oral health.

All assessments and the provision of oral hygiene instruction will be provided by a single dental clinician.

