The images captured will be downloaded and form a pictorial report of the health of the patient's mouth which will be provided to the patient. For those participants allocated to receive the pictorial report + verbal OHI (test group), the images and video captured will be explained to the patient so they can understand their current oral health. Participants assigned to receive standard verbal OHI alone will not be shown or have a review of the images collected by the intra-oral camera or be provided with a pictorial report of their current oral hygiene at Visit 1, however they will receive this at the end of the study.

For all participants, oral hygiene instruction will then be provided by a single dental clinician. This will be a different clinician from the clinician performing the dental assessments and scans of the mouth. For participants assigned to receive the pictorial report + verbal OHI (test group), they will be provided with oral hygiene instruction, a leaflet on oral health and a mouth mirror to use at home.

Participants will also receive questionnaires on their current oral hygiene practices and attitudes to oral health.

An appointment will be made for the patient to return to the study site in 4 weeks and they will be assessed for plaque levels and gingival health and a further scan of their mouth taken. For those participants assigned to receive the pictorial + verbal OHI, a pictorial report will be generated and reviewed alongside their initial report with the patient and advice provided for ongoing oral health maintenance.

For those participants who were assigned to receive standard verbal OHI alone, following the completion of study assessments at Visit 2, the dental clinician will then review the images of their mouth captured at both Visit 1 and Visit 2 and provide the patient with a copy of their pictorial report from both Visits to take away with them. These participants will also be provided with a mouth mirror and an information leaflet regarding the importance of maintaining good oral health along with advice for their individual ongoing oral health maintenance.

For each patient recruited to the study, they will be required to attend 2 study visits with the research team. The appointments are as outlined below:

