#### Visit 1: (Approximately 40 minutes)

- Consent
- Oral hard and soft tissue examination
- Eligibility

- Patient assessment of standard mouth images with dentist to look at the appearance of healthy vs non- healthy mouths (See Appendix 3)
- Intra-oral scan of patient's mouth and assessment of plaque download report for patient to take away (Appendix 5)
- Plaque and gingival health assessments (See Appendix 4)
- Randomisation
- Completion of questionnaire with regards to current oral health/hygiene practices (Part A) and patients' attitudes to oral health (Part B) (See Appendix 1 Parts a and b)
- Provision of OHI instruction by dentist depending on randomisation either standard verbal OHI **or** enhanced OHI (pictorial + verbal OHI) with a detailed pictorial report for the patient
- Provision of OH leaflet and mouth mirror for participants use at home for those participants assigned to the pictorial + verbal OHI group only.

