#### Study dental assessments

The intra-oral camera will record images of the teeth and gums of the patient which will be downloaded to form a pictorial report tailored to the patient. The intra-oral camera also detects and measures plaque levels present on the surface of teeth. This function will be used to assess the plaque levels present on the upper 3-3) prior to any dye being placed on the participants teeth.

The baseline and 4-week plaque and gingival health assessments will be performed by a single dental clinician. Teeth in the upper 3-3 area will be scanned using the intra-oral camera. The teeth for gingival health and plaque assessment within the study will be 2 suitable teeth within the upper 3-3 region as determined by the study clinician. The same 2 teeth will be assessed by the clinician at Visit 1 and Visit 2 for plaque and gingival health.

Plaque scores will be recorded at Visit 1 and 2 following the method established by O'Leary et al (1972). Plaque will be scored using a 2-point code (buccal and lingual/palatal) where NO (0) = no plaque and YES (1) = presence of plaque.

Gingival health will be assessed using the Modified Gingival Index (MGI) (Lobene, 1986) and the gingival bleeding index (BOP) as described by Ainamo & Bay (1975). The MGI index is a non-invasive visual evaluation of gingival health. Each site (2 per tooth) will be classified as healthy or exhibiting gingivitis. If the site exhibits gingivitis the MGI index will be used to assess the degree of gingival inflammation at 2 sites (buccal and lingual/palatal) of each suitable scorable teeth and scored on a 5-point scale. Gum health will also be assessed by recording bleeding on probing. A periodontal probe with a 0.5 mm diameter tip is inserted into the gingival crevice and swept from distal to mesial, around the tooth at an angle of approximately 60° while in contact with the sulcular epithelium. For each tooth assessed, a binary recording of either YES (bleeding observed) or NO (no bleeding observed) for bleeding will be made at 4 sites per tooth. The proportion of bleeding sites compared to all examined sites will provide the percentage of bleeding per participant.

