#### Outcomes

#### **Primary Objectives**

• To evaluate patient gingival health and plaque levels prior and following the provision of a pictorial report and tailored OHI over a 4-week.

Gingival health changes from Visit 1 (baseline) to Visit 2 (week 4) will be measured using a 5-point MGI scale (Lobene, 1986) and bleeding on probing will be measured using a 2 point scale, 'YES(1)' or 'NO (0)'. Changes from Visit 1 (baseline) to Visit 2 (week 4) in plaque scores will be measured using the O'Leary et al (1972) 2 point scale, 'YES(1)' or 'NO (0)'.

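### The protocol separates the oral hygiene instructor from the outcome assessor in one section and merges them in another; under the merged rule the Visit 2 assessor knows the allocation

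*Protocol*

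**What the plan says.** The protocol describes who instructs and who assesses in three places.

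- **Study Design.** On instruction: "For all participants, oral hygiene instruction will then be provided by a single dental clinician". The next sentence separates the roles: "This will be a different clinician from the clinician performing the dental assessments and scans of the mouth".
- **Visit 2, closing sentence.** "All assessments and the provision of oral hygiene instruction will be provided by a single dental clinician".
- **Study dental assessments.** "The baseline and 4-week plaque and gingival health assessments will be performed by a single dental clinician". This section does not say who gives the instruction.

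Two further statements matter. The Visit 1 list makes the instruction arm-specific: "Provision of OHI instruction by dentist depending on randomisation either standard verbal OHI", or the enhanced version with the pictorial report. The Outcomes section places the examiner's scores under the primary objectives: "Gingival health changes from Visit 1 (baseline) to Visit 2 (week 4) will be measured using a 5-point MGI scale", with yes/no bleeding and yes/no plaque alongside.

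**The concern.** Staff reading Study Design would assign two clinicians; staff reading the Visit 2 section would assign one. The choice decides whether the person scoring at 4 weeks knows the arm. Participants cannot be masked to receiving a report, so the examiner is the only point at which knowledge of allocation could be kept away from the clinical outcomes.

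An examiner who knows the arm may grade a borderline site differently in one group. MGI is the most exposed: "The MGI index is a non-invasive visual evaluation of gingival health". Plaque after dye and bleeding after probing are yes/no calls and leave less room, but the same examiner makes them. Bias of this kind cannot be removed in the analysis.

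**Working it through.** **Step 1: set the rules side by side.**

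| Protocol section | Who gives OHI | Who assesses | Same person? |
|---|---|---|---|
| Study Design | One clinician for all participants | A different clinician | No |
| Visit 2, closing sentence | One clinician | That same clinician | Yes |
| Study dental assessments | Not mentioned | One clinician at both visits | Open |

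The first two rows exclude each other. The third fits either, so it neither adds to the conflict nor settles it.

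**Step 2: follow the merged rule through the visits.** Randomisation comes before instruction at Visit 1, and the instruction depends on the arm, so whoever gives it knows the arm. If that person makes all assessments, the MGI, plaque and bleeding scores at Visit 2 are made with knowledge of allocation.

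**Step 3: follow the separated rule.** The assessor scans and scores at Visit 1 before randomisation and does not give the instruction. The assessor could therefore be unaware of the arm at Visit 2, but the protocol does not say so. Two gaps remain under this rule:

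- Study Design does not say who explains the images to test participants at Visit 1.
- Study Design places the Visit 2 report review after the assessments explicitly for the control arm only. The Visit 2 list does put handing over the report after the final scores.

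**Step 4: an illustration of size, resting on assumptions.** The protocol gives no rate of differential scoring, so the rates below are assumed. The plaque score is taken as the proportion of sites with plaque, which is also an assumption.

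- Sites per participant: 2 teeth × 2 sites = 4 (Study dental assessments).
- Weight of one site: 1/4 = 0.25.
- Shift in the arm difference = 0.25 × share of test participants with one site scored differently.
- Share of one-third: 0.25 × 1/3 = 0.083.
- Share of one-half: 0.25 × 1/2 = 0.125.
- Share of two-thirds: 0.25 × 2/3 = 0.167.

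The comparison is the precision in the Sample Size section, which gives two values. The text says about 0.16 either side of the observed difference. The example interval, 0.607 to 0.772, has half-width (0.772 − 0.607)/2 = 0.0825.

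- Share needed to match the example: 0.0825/0.25 = 0.33.
- Share needed to match the text: 0.16/0.25 = 0.64.

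**The case against.** The best defence is that the Visit 2 sentence compresses two rules stated elsewhere: one clinician for all instruction, and one for all assessments. A drafting slip is plausible. But the sentence puts both tasks under one clinician, and staff act on the text. Another reading limits it to Visit 2, where control participants receive tailored advice after their scores. The conflict then still remains if the single instructor of Study Design is the same person at both visits.

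Several limits on the point do stand.

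- A reader might infer that the protocol breaks its own blind. It does not: no assessor blind is declared anywhere. Separating the roles makes masking possible without stating it.
- A reader might infer that the three outcomes are equally subjective. They are not: MGI is a visual grade, while dye-disclosed plaque and bleeding on probing are binary and less open to drift.
- A reader might infer that an examiner aware of the arm would move the result by more than the trial's precision. The documents do not show this. The rates are assumed, and against about 0.16 neither 0.083 nor 0.125 exceeds it.
- Order at Visit 2 is already partly protected, as noted above. Further measures, such as keeping the assessor out of randomisation or away from the questionnaire, would be design preferences and not corrections of this error.

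The study has 20 participants and aims at estimation rather than testing. That lowers the stakes of a false positive, but a biased estimate is no more useful for being called an estimate. The camera company's funding is a fact of the protocol and is no evidence of bias.

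**Conclusion.** The contradiction is real on the plain wording, and nothing else in the protocol resolves it. Under the Visit 2 sentence, the 4-week primary outcomes are scored by someone who knows the allocation. Under the Study Design rule they need not be, although the protocol does not commit to that.

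The harm is conditional on the Visit 2 sentence being followed, and its size is unknown. The range of 0.083 to 0.167 only shows that, with four plaque sites per participant and 10 participants per arm, a modest number of altered calls is of the same order as the stated precision. The finding does not depend on that illustration. It should be corrected before recruitment because it bears on every clinical primary outcome.

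**What to change.** Replace the closing sentence of the Visit 2 section with the Study Design rule: one clinician does the scans and scores at both visits, and a different clinician gives the instruction and explains the reports. Add two statements:

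1. The assessor is not told the allocation.
2. In both arms, Visit 2 scores are recorded before any report is reviewed.

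If Study Design reflects the real staffing, this costs a wording change and no extra staff. If one clinician will in fact do everything, a second would be needed, possibly at more than one of the listed locations. Should that not be feasible, the protocol should amend Study Design to match, state that the assessor is aware of allocation, and give this as a limitation.

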#### Study Recruitment

The study will recruit approximately 20 healthy dentate female and male participants aged 18 or over. The Clinical Trials Unit has a database of previous study participants who have expressed an interest in taking part in more studies. These contacts will be approached to take part.

#### Inclusion Criteria

- Be aged 18 years and over, of either gender and in good health.
- Participants should be dentate with a minimum of 18 scorable teeth, with at least 4 teeth in the upper anterior sextant.
- Participants should be without removable dental prostheses or fixed or removable orthodontic appliances
- Be willing and competent (verbally and cognitively) to give written informed consent and complete a medical history form.
- Be willing and physically able to carry out all study procedures.
- Have an MGI score of ≥1 on at least one of the 2 identified teeth for assessment.

#### **Exclusion Criteria**

- Medical condition and/or regular use of any medication which might affect the outcome of the study, as determined by the study dentist, principally a course of anti-inflammatory, antimicrobial or statin drugs
- Participants with secondary modifying factors in relation to periodontal disease (e.g. immunocompromised individuals and smokers, including vaping nicotine with e-cigarettes).
- Any participant who, in the judgement of the investigator, should not participate in the study.
- An employee of the research team at the study site.

#### Study dental assessments

The intra-oral camera will record images of the teeth and gums of the patient which will be downloaded to form a pictorial report tailored to the patient. The intra-oral camera also detects and measures plaque levels present on the surface of teeth. This function will be used to assess the plaque levels present on the upper 3-3) prior to any dye being placed on the participants teeth.

The baseline and 4-week plaque and gingival health assessments will be performed by a single dental clinician. Teeth in the upper 3-3 area will be scanned using the intra-oral camera. The teeth for gingival health and plaque assessment within the study will be 2 suitable teeth within the upper 3-3 region as determined by the study clinician. The same 2 teeth will be assessed by the clinician at Visit 1 and Visit 2 for plaque and gingival health.

Plaque scores will be recorded at Visit 1 and 2 following the method established by O'Leary et al (1972). Plaque will be scored using a 2-point code (buccal and lingual/palatal) where NO (0) = no plaque and YES (1) = presence of plaque.

Gingival health will be assessed using the Modified Gingival Index (MGI) (Lobene, 1986) and the gingival bleeding index (BOP) as described by Ainamo & Bay (1975). The MGI index is a non-invasive visual evaluation of gingival health. Each site (2 per tooth) will be classified as healthy or exhibiting gingivitis. If the site exhibits gingivitis the MGI index will be used to assess the degree of gingival inflammation at 2 sites (buccal and lingual/palatal) of each suitable scorable teeth and scored on a 5-point scale. Gum health will also be assessed by recording bleeding on probing. A periodontal probe with a 0.5 mm diameter tip is inserted into the gingival crevice and swept from distal to mesial, around the tooth at an angle of approximately 60° while in contact with the sulcular epithelium. For each tooth assessed, a binary recording of either YES (bleeding observed) or NO (no bleeding observed) for bleeding will be made at 4 sites per tooth. The proportion of bleeding sites compared to all examined sites will provide the percentage of bleeding per participant.

#### Items provided to patient

The items to be supplied to the participants are detailed below:

- Pictorial record and report of their current oral health at Visit 1 and Visit 2
- Patient Information Leaflet on Oral Health at Visit 1
- Participant own use intra-oral mirror at Visit 1

For participants assigned to receive standard verbal OHI alone, then they will be provided with all items following completion of all study assessments at Visit 2.

#### Outcomes

#### **Primary Objectives**

• To evaluate patient gingival health and plaque levels prior and following the provision of a pictorial report and tailored OHI over a 4-week.

Gingival health changes from Visit 1 (baseline) to Visit 2 (week 4) will be measured using a 5-point MGI scale (Lobene, 1986) and bleeding on probing will be measured using a 2 point scale, 'YES(1)' or 'NO (0)'. Changes from Visit 1 (baseline) to Visit 2 (week 4) in plaque scores will be measured using the O'Leary et al (1972) 2 point scale, 'YES(1)' or 'NO (0)'.

#### Secondary Objectives

- Patient perceptions of effectiveness of a having a pictorial report of their oral health as part of their dental care at Visit 1 and Visit 2
- Patient attitudes to oral health measured at Visit 1 and Visit 2
- Participants understanding of oral health vs oral disease at Visit 1 and Visit 2
- Assessment of the accuracy of the intra-oral camera's ability to assess plaque levels compared to the clinician using traditional techniques using dye

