#### Study Design

The study will be a parallel, randomised (1:1 ratio) 2 treatment, single centre study. The study sites will be the University of Bristol Dental School and Hospital including the South Bristol Community Hospital outreach centre, and the general dental practice Redland Park Dental Surgery. The study will be conducted by the Clinical Trials Unit team members who are part of Bristol Dental School.

At Visit 1, following provision of informed consent and confirmation of eligibility to take part in the study, participants will be provided with a questionnaire to complete regarding gum (gingival) health and then shown standard pictures of teeth and gingivae. They will be asked to indicate whether they think the pictures demonstrate oral health or oral disease and which they think represents their current oral health.

The participants will undergo an oral hard and soft tissue examination.

An intra-oral diagnostic camera will then be used by the clinician to take an intra-oral scan including images and a video of the patient's mouth. The images and video captured will be downloaded and a pictorial report prepared of their oral health. The camera software has the ability to detect plaque on the teeth and this will also be used to assess the levels of plaque present on the participant's teeth.

The study dentist will carry out a gum health examination (Modified Gingival Index, MGI) for the participant and will then measure the amount of plaque present using a traditional technique involving placing dye (food colouring) onto the surface of the teeth which highlights plaque (O'Leary et al 1972).

Participants will be randomised by study staff to one of 2 treatment groups (Control group - standard verbal oral health instructions (verbal OHI) or Test group – pictorial report + verbal oral health instructions (picture + verbal OHI) using a predetermined randomisation schedule.

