# **Appendix 2: Patient Questionnaires for Visit 2**

# Patient Oral Health Questionnaire - Visit 2 – Part A

If you have trouble completing this questionnaire, please ask a member of staff to assist you.

**1.** How many times per day do you now regularly brush your teeth? (*Please tick one box only*)

	Less than once a day					
	Once a day	1				
	Twice a day					
	More than twice a day	7				
2.	. When do you now normally brush	n your teetl	h? (Please tick all that a	pply )		
	In the morning					
	In the evening					
	During the day					
3.	Do you usually brush your teeth (F Before breakfast	Please tick	one box only)			
	Neither before or after breakfast	H				
	After breakfast	H				
	Both before and after breakfast	H				
4.	Do your gums bleed now when yo	bu brush yc	our teeth?			
	NO					
5.	. Do you think you have bad brea	ath now?				
	NO					
6.	. Do you use any of the following ac	dditional te	eeth cleaning aids now f	? (examples )	are shown belo	w,
pie	Dental Floss Flosset	ave usea or ttes	Single tufted brush	e, tick none) Interdental	hrushses (e ø Tel	Pe)
	Air flosser (e.g Phillips Airflos	oss Plus)	Water flosser (e.g Wate	erpik)	None	
			And and a second	-	X	

Page 16 of 23

- 7. If you have indicated you have used an additional cleaning aid, how often did you use them?
  Daily

  Weekly
  Occasionally

  8. Are you currently concerned about your oral health?

  YES
  NO

  9. Has your diet changed since you started the study with us?

  Yes
  No
  No
  No
  No
  No
  No
  No
  No
- **10.** Was the pictorial report of your oral health provided in this study useful for you?

.....

Very useful	
Fairly useful	
Neither useful or not useful	
Not useful	
Not sure	
How often did you refer o your pi	ctorial report provided in this study?
Daily	

How?...

11.

Weekly

Didn't refer to it

12. Are you currently concerned about your oral health?

YES	
NO	

**14.** If yes, what are your concerns?

Condition of teeth	
Function of teeth	
Appearance	
Breath	
Sensitivity	
Other/Not sure	
None	

**15.** How would you rate your current oral health now?

Excellent	
Very good	
Good	
Fair	
Poor	
Not sure	

16. Are you motivated in maintaining oral health now?

	Very motivated	
	Fairly motivated	
	Neither motivated or not motivated	
	Not motivated	
	Not sure	
17.	Has your motivation to maintain you	r oral health changed since you started the study with us?
	Yes N	Not sure
	How?	

so

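### Understanding of health versus disease is an outcome at both visits but is scheduled only before randomisation, and the Visit 2 items on the pictorial report are put to controls who have not yet had one

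*Protocol*

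**What the plan says.** **Understanding.** In the Protocol, the secondary objectives under Outcomes include "Participants understanding of oral health vs oral disease at Visit 1 and Visit 2". The Study Design section describes the matching task at Visit 1, where participants see standard pictures: "They will be asked to indicate whether they think the pictures demonstrate oral health or oral disease". The Visit 1 list carries it as "Patient assessment of standard mouth images with dentist" and points to Appendix 3, which holds three images. In the Visit 2 list the only step that participants complete themselves is "Completion of questionnaire with regards to current oral health/hygiene practices (Part A) and attitudes to oral health (Part B). (See Appendix 2").

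**Perception of the report.** The same part of Outcomes lists patients' perceptions of the effectiveness of "having a pictorial report of their oral health as part of their dental care at Visit 1 and Visit 2". The visible items on this are in Visit 2 Part A (Appendix 2). Item 10 asks "Was the pictorial report of your oral health provided in this study useful for you", and item 11 asks how often the participant referred to the report. Study Design and Items provided to patient both say that controls get their report only once the Visit 2 assessments are complete.

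**Analysis.** Statistical Analyses says that each secondary outcome will be analysed in a similar way to the primary outcome, through a generalized linear model with confidence intervals and p-values. The primary analysis estimates the difference between arms in change from baseline.

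**The concern.** An outcome defined at two visits needs its instrument at both. If the image task is done only before randomisation, it describes the sample at entry and says nothing about whether the report improved participants' ability to tell health from disease. That is a natural question for a proof-of-principle study of a pictorial education tool. No analysis plan can supply data that the schedule never collects.

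The perception items raise a different problem. Someone who has not received a report cannot rate its usefulness or say how often they consulted it in any way comparable with someone who has. If the general rule for secondary outcomes is applied to these items, test-arm opinions of the report are set against control answers that refer to nothing. Two of the four listed secondary outcomes are affected; the primary outcome is not.

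**Working it through.** No sample size, power or error-rate figure underlies this point. The check compares the outcome definitions with the visit lists and the instruments, then counts the values that the schedule can yield. The one numerical input is the planned 10 participants per group, 20 in total (Randomisation; Sample Size).

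**Step 1: where the image task is scheduled.**

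| Place in the Protocol | Image task? |
|---|---|
| Study Design, Visit 1 narrative | Yes |
| Visit 1 list | Yes, fourth step; randomisation is seventh |
| Study Design, week-4 narrative | No |
| Visit 2 list | No; cites Appendix 2 only |
| Appendix 2, Visit 2 Parts A and B | No |
| Appendix 3 form | Carries no visit label |

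Values available: 20 of 20 at Visit 1 and 0 of 20 at Visit 2, so 0 participants have a change score. The Visit 1 values precede randomisation, so they cannot carry an intervention effect.

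**Step 2: could another instrument serve?** Part B asks at both visits how serious bleeding gums are and how likely untreated bleeding is to lead to gum disease. These are 1-to-10 ratings on a form titled as an attitudes questionnaire, and attitudes are a separate secondary outcome. They do not ask the participant to distinguish a healthy mouth from a diseased one.

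**Step 3: when controls meet items 10 and 11.** In the Visit 2 list the questionnaire is the third step, provision of the report the sixth, and the controls' review of their reports the seventh. The point does not rest on list order alone: Study Design and Items provided to patient place the controls' report after the Visit 2 assessments. One Visit 2 form is shown, with no arm-specific version and no visible instruction to skip.

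Answers to items 10 and 11 at Visit 2: 10 of 20 (test arm) concern a report received four weeks before; 10 of 20 (controls) concern a report not yet received. The number of controls with an interpretable value is 10 − 10 = 0, so there is nothing to contrast with the test arm.

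**Step 4: perception at Visit 1.** No item on the report is visible in Appendix 1, Part A or Part B. In the Visit 1 list the questionnaires (eighth step) also come before the instruction and report (ninth step). If the outcome means measurement at both visits, 0 of 20 participants have a Visit 1 value. Whether it means that is taken up under the objection.

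**The case against.** **The outcome itself may be instruction enough.** Outcomes calls for understanding at Visit 2, and the Appendix 3 form could be used at either visit. Site staff might repeat it, so 0 of 20 assumes that they work from the visit list. That is fair, but the list is what a site follows, and the week-4 narrative and Appendix 2 agree with the list.

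**No sentence ties this outcome to Appendix 3 alone.** True; the link is an inference from content. It stands, because no other form asks for the distinction between health and disease.

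**Neither outcome is lost altogether.** A reader might infer that both are unobtainable. The Protocol does not support that: understanding at Visit 1 and test-arm perception at Visit 2 can be collected as written. What is missing is the follow-up value in one case and a valid control value in the other.

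**The perception bullet need not require a Visit 1 measurement.** A reader might take the lack of Visit 1 perception items as a contradiction. But in "pictorial report of their oral health as part of their dental care at Visit 1 and Visit 2" the timing may attach to the report, which Items provided to patient says is supplied at both visits. The attitudes bullet says expressly that attitudes are measured at the two visits; the perception bullet does not. This objection stands: the wording is ambiguous.

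**The bias has no certain direction.** A reader might infer that the comparison favours the report by construction. That assumes how controls would answer. Item 10 offers a not-sure option, controls could leave the items blank, and for item 11 saying that they did not refer to a report would be literally true. An analyst might also restrict the items to the test arm, which an analysis plan could specify. Only the absence of a valid control value is established.

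**Parts of the questionnaires are damaged in the available text.** Visit 1 Part A item 13 cannot be read; its place after the cleaning-aid question, and the parallel Visit 2 item 7, suggest that it asks how often the aids are used. A skip instruction or a not-applicable box at items 10 and 11 cannot be wholly excluded.

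**Conclusion.** The point holds in two parts, and both should be corrected.

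1. Understanding of health versus disease is defined at two visits and scheduled at one. Followed as written, there are 0 of 20 post-intervention values, and neither change nor an arm effect can be estimated. This assumes that the visit list governs conduct and that Appendix 3 is the instrument for this outcome.
2. Items 10 and 11 are put to all participants as shown, while all 10 planned controls are still without a report. A between-arm analysis under the general rule for secondary outcomes would have no valid control value. This assumes that the form as visible has no arm-specific routing. The direction of any artefact is uncertain.

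The timing phrase in the perception outcome is a matter for clarification, not a demonstrated contradiction. These are secondary outcomes in a pilot sized for estimating a difference in plaque scores, and that analysis is untouched.

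**What to change.** - Add the Appendix 3 image task to the Visit 2 list, before any report is reviewed with the participant, and cite the appendix there. Cost: a few minutes per participant, using a form that already exists.
- Restrict items 10 and 11 of Visit 2 Part A to the test arm and summarise them descriptively. If control views are wanted, ask controls a usefulness item only after they have received their reports at the end of Visit 2. In either case, state that no between-arm test will be made on these items. Cost: a routing line or a short extra item.
- In Outcomes, say whether the two-visit timing in the perception bullet refers to the report or to the measurement. If it is the measurement, Visit 1 needs an item on the report placed after the report has been given; if it is the report, reword the bullet and name Visit 2 as the time of measurement. Cost: wording, plus one item under the first reading.
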